6.2 Trial hypothesis and PICOT

In UK military veterans (P) the remotely delivered FIRST Protocol (I) compared to waiting list control (C) is clinically and statistically effective in reducing PTSD symptoms by the minimal clinically important difference (O) at 20 weeks (T).

6.3 Primary endpoints

1) PTSD symptom severity assessed by the PCL-5.

6.4 Secondary endpoints

1) PTSD diagnosis assessed by the CAPS-5.

2) The impact of the person's mental health on work, home, social and private leisure activities and interpersonal relationships assessed by the *Work and Social Adjustment Scale*.

- 3) Depression assessed by The Patient Health Questionnaire (PHQ9).
- 4) Health status assessed by The EQ5D-5L.
- 5) Self-rated self-esteem assessed by The Self-esteem scale.

7 Mechanisms study

Objective: To test hypotheses for the FIRST protocol's mechanistic pathways by which it achieves its effects.

Hypothesis: The amelioration of one or more of the proposed mechanistic outcomes will align with a reduction of PTSD and CPTSD symptoms found in the trial outcomes.

The impact of understanding mechanisms is that NHS and other therapists can be confident in using the FIRST protocol to treat PTSD and CPTSD and it should be rolled out in treating the veteran and other PTSD populations. Furthermore, if these mechanisms explain the causal pathway by which the FIRST protocol achieves effective reduction of PTSD and CPTSD symptoms, then it follows that FIRST can be implemented in populations who do not meet PTSD and CPTSD criteria but nonetheless have a trauma history and have distressing PTSD symptoms. Specific mechanistic hypothesis at the psychological and symptom level are discussed below and visually presented in table 1 and figure 1.

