7.2 Research impact

This research will be the first to test therapies incorporating NLP and cognitive techniques process under robust trial conditions and increase understanding for its mechanistic pathway. It will thereby deliver evidence to the neurocognitive, psychiatric and psychology clinical communities on how these, almost always, brief interventions could be understood and targeted in clinical practice. Understanding mechanisms using well documented science is key to enabling these communities to be curious about, and develop greater trust in, therapies incorporating NLP techniques and reconsolidation process.

Table 1. Primary hypotheses. Testing these will allow us to achieve our primary objective of determining what specific psychological mechanisms explain the FIRST protocol's effectiveness.

Hypothesis [H]	Mechanism	Level and prediction (P=psychological hypothesis; S=symptom hypothesis)	Executive function	Psychological Assessment Task	PTSD Symptoms
H1: FIRST improves ability to remember and reproduce emotionally free neutral memories	Emotionally processed or integrated traumatic memories reduce dissociation and PTSD symptoms	At psychological level (P1): The treatment group compared to controls will experience improved trauma memories	Memory	The Trauma Memory Quality Questionnaire (TMQQ)	Dissociation, intrusions and re-experience PCL-5 Dissociative Experiences Scale- II (DES- II)
H2: FIRST improves ability to resist interference from negative stimuli resulting to improved attentional focus and inhibitory control	Alterations in ability to resist interference from distracting stimuli, and therefore effectively move attention away from trauma.	At psychological level (P2): The treatment group compared to controls will experience improved attention focus and inhibitory control	Selective Attention: Attentional facilitation, interference and avoidance Inhibitory control	Emotional Stroop task	Hypervigilance- and arousal PCL-5 (DES-II)
H3: FIRST improves regulation of emotions in relation to the traumatic event	Improves ability for regulating emotions and PTSD	At psychological level (P3): The treatment group compared to the controls will show improved self-regulation	Emotional regulation	Cognitive Emotion Regulation Questionnaire– Short (CERQ- Short form)	Aggression, irritability and reactivity PCL-5 DES-II

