10.9 Mechanisms study outcomes

The Emotional Stroop task is the mechanisms study primary outcome due to evidence on the neural interaction between emotions and cognitive control (attention processes, working memory and reaction conflict or inhibition) [96].

1) Attentional bias: a) The emotional Stroop task will be used to assess attentiona bias. The stimuli will use coloured words (red, blue, green, or yellow) shown one at a time in the centre of a computer screen, using all capital letters, on a black background. Colours will not repeat on consecutive words and will equally used throughout all trials. Three types of word stimuli will be used: a) combat-related words, b) negative words, and c) neutral words. The combat-related threat list is to be personally-relevant to combat veterans and is comprised of words related to things encountered in a warzone (e.g., bomb, seize), negative list contains words that were negative in valence, but not related to combat (e.g., tax, witch). The neutral list contains words that are non-

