The SAP will also outline the Mediation analysis to test any predefined mediator. [116] Analyses will be conducted using the STATA 17 software. iii) The Mechanisms study primary outcome analysis will estimate the difference in Emotional Stroop task reaction time at 12 weeks between the two treatment groups (FIRST vs. WL). A mixed ANOVA test will be used to measure the effect of emotional stroop task reaction time between T1 & T3. Means and standard deviations will be reported. The Statistical Analysis Plan will outline the analysis of all the other mechanism outcomes.

We do not anticipate that missing data will be more than what has been accounted for in the trial sample size estimation. The level and pattern of the missing data in the baseline variables and outcomes will be investigated. The likely causes of any missingness will be summarised. If data are missing at random, multiple imputation will be used. If, when the missing data are analysed, they present another pattern other than missing at random, we will explore other methods of imputation.

iv) Maintenance of effect will be assessed as an exploratory analysis. Clinical outcome data at 52weeks will be compared to the 20-week trial final endpoint data to determine whether the FIRST group maintained the 20-week PCL-5 scores. The 52-week experimental arm data will also be contrasted with published treatment effect evidence from NICE recommended TF-CBT therapy at the same time point e.g. [58, 59]. This evidence will be compared with FIRST maintenance of effect data to inform NHS dissemination decisions and possibly generate future research questions using FIRST in additional populations living with PTSD to broaden our understanding of the impact of FIRST.

12 Project management

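### The protocol makes all five mechanism hypotheses primary in Table 1 but only the Emotional Stroop task primary in 10.9, Table 7 and section 11, and section 7 is met by any one of them

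*Protocol*

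**What the plan says.** Section 7 (Hypothesis) states: "The amelioration of one or more of the proposed mechanistic outcomes will align with a reduction of PTSD and CPTSD symptoms". The sentence goes on to tie that reduction to the results of the trial itself. The same section then describes the impact of understanding mechanisms: "NHS and other therapists can be confident in using the FIRST protocol to treat PTSD and CPTSD".

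The table in section 7.2 is introduced with "Table 1. Primary hypotheses. Testing these will allow us to achieve our primary objective of determining what specific psychological mechanisms explain". It lists H1 to H5, each with a treatment-versus-control prediction on its own measures: TMQQ (H1), Emotional Stroop (H2), CERQ-Short (H3), the Post-traumatic Cognitions Inventory, AMT and Self-esteem scale (H4), and digits forward and backward (H5). A last row, S1, predicts that change in the mechanism measures will go with reductions in PTSD and dissociation symptoms.

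Section 10.9 states: "The Emotional Stroop task is the mechanisms study primary outcome due to evidence on the neural interaction between emotions and cognitive control". Table 7 labels the same task as the mechanisms primary outcome, and section 11 (iii) agrees: "The Mechanisms study primary outcome analysis will estimate the difference in Emotional Stroop task reaction time at 12 weeks between the two treatment groups". Section 11 leaves the analysis of the other mechanism outcomes to the SAP.

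**The concern.** The status of H1, H3, H4 and H5 is fixed in two incompatible ways. Under Table 1 they are primary and carry the mechanisms objective. Under 10.9, Table 7 and section 11 they are not. Section 7 sides with the looser reading, since any one of the outcomes can satisfy it.

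This matters most when the Stroop comparison shows nothing and another measure reaches nominal significance in the favourable direction. One reader reports a negative mechanisms study and another reports a supported mechanism, and both can point to the protocol. The situation is realistic: against a waiting list, a therapy could lower PCL-5 without acting through any of the proposed pathways, and a mechanisms study exists to detect that case.

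Deferring the analysis to the SAP does not settle the matter. What is deferred is how the other outcomes are analysed. Their status is already stated in the protocol, twice and differently.

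**Working it through.** **The plan's own figure.** The protocol gives no error rate or sample size for the mechanisms study. Its only stated 5% level belongs to the PCL-5 calculation in 10.6. That calculation reproduces: n per group = 2(1.96 + 1.2816)² × 20²/10² = 84.1, or 85.03 with the t distribution, rounded up to 86. This gives 172 in total, and 172/0.8 = 215. A per-test level for the mechanism measures therefore has to be assumed.

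**Passages side by side.**

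| Place | What is primary for mechanisms |
|---|---|
| Section 7, Hypothesis | any one or more outcomes, aligned with symptom reduction |
| Table 1 | H1, H2, H3, H4 and H5 |
| 10.9, Table 7, section 11 (iii) | Emotional Stroop (H2) only |

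**How many tests.** One score per hypothesis gives 5. Table 7 marks 7 instruments (M): Stroop, AMT, digit task, TMQQ, CERQ-Short, PTCI-9 and DES-II. Adding the Self-esteem scale (listed under H4), or scoring digits forward and backward separately as 10.9 describes, gives 8; doing both gives 9.

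**Scenario.** FIRST lowers PCL-5 but affects no mechanism measure. Improvement is directional, so only favourable results count, at an assumed 2.5% each.

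**Independent tests.** The chance of at least one favourable result is 1 − 0.975^k:
- k = 5: 11.9%
- k = 7: 16.2%
- k = 8: 18.3%
- k = 9: 20.4%

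**Correlated tests.** With a common correlation ρ between the test statistics (assumed; the protocol gives none), the chance is 1 − ∫ Φ((1.96 − √ρ·z)/√(1 − ρ))^k φ(z) dz:

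| k | ρ = 0 | 0.3 | 0.5 | 0.7 | 0.8 |
|---|---|---|---|---|---|
| 5 | 11.9% | 10.5% | 9.1% | 7.4% | 6.4% |
| 7 | 16.2% | 13.7% | 11.5% | 8.9% | 7.4% |
| 8 | 18.3% | 15.2% | 12.5% | 9.5% | 7.9% |
| 9 | 20.4% | 16.5% | 13.5% | 10.1% | 8.3% |

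The single Stroop test gives 2.5%.

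**The conflicting result.** No favourable Stroop result with a favourable hit elsewhere has probability P(any favourable) − 2.5%:
- Five tests: 6.4 − 2.5 = 3.9% to 11.9 − 2.5 = 9.4%.
- Seven to nine measures: 7.4 − 2.5 = 4.9% to 20.4 − 2.5 = 17.9%.

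**Therapy null on PCL-5 as well.** If the aligned reduction is read as a significant favourable PCL-5 result, simulation gives a joint chance of about 0.4% to 1.9% (seven to nine measures, ρ from 0 to 0.7).

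**After the fix.** Stroop alone: 5% two-sided, 2.5% favourable. Five primaries at the Bonferroni level of 0.05/5 = 0.01: 1 − 0.99^5 = 4.9% under independence. Holm controls the same family-wise rate and is never less powerful.

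**The case against.** The strongest objection is that the operative text is consistent. Section 10.9, Table 7 and section 11 all name one primary outcome with one comparison at 12 weeks. The section 7 sentence is a hypothesis and not a formal success rule, and multiplicity detail for the other outcomes may properly sit in the SAP. The absence of such detail is indeed no fault here. But Table 1 is also current protocol text, and its heading and introduction cannot be squared with a single primary.

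A reader might infer something stronger: that an entirely ineffective therapy would be credited with a mechanism in a fifth to a third of trials or more. The document does not support that, for three reasons.
- The section 7 sentence goes on to require alignment with symptom reduction found in the trial, and S1 asks that mechanism change predict it. A therapy null on everything would rarely qualify.
- Figures such as 1 − 0.95^9 = 37% count significant worsening as support, although the hypothesis speaks of improvement.
- Inflating the count by testing all nine CERQ-Short subscales has no basis. Table 1 lists the instrument as one assessment, and no passage plans subscale tests.

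It would also be too strong to say that roll-out hangs on one nominal p-value. The confidence statement describes the impact of understanding mechanisms, and the extension to people below diagnostic criteria is conditional on the mechanisms explaining the causal pathway.

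The further conditions are, however, loosely specified. Alignment has no stated test. S1 refers to change between time 1 and time 2, while Table 7 puts Time 2 at six weeks and collects the mechanisms battery only at baseline and 12 weeks.

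**Conclusion.** The contradiction is real and rests on the text alone. Its numerical consequence is moderate: a chance favourable signal in about 6-12% of trials for five tests and 7-20% for seven to nine measures, against 2.5% for the Stroop task. The specific conflict, Stroop null with a hit elsewhere, arises by chance in about 4-9% and 5-18% respectively.

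The per-test level, the common correlation and the count of measures are assumptions. The figures hold only where FIRST works on PCL-5 and no mechanism measure is affected. They are upper figures, because the alignment and S1 conditions come on top. The trial's PCL-5 conclusion is not touched. The point is worth correcting because the same data could be reported as negative or supportive, and the correction is cheap.

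**What to change.** Choose one rule and state it in section 7, Table 1, 10.9 and section 11.

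- **Option A.** Retitle Table 1 so that H2 (Emotional Stroop, 12 weeks) is primary. Make H1, H3, H4 and H5 secondary with one named score each and a Holm adjustment (first step 0.05/4 = 0.0125), or label them exploratory.
- **Option B.** Keep all five primary, with one named score each and Holm across the five (first step 0.05/5 = 0.01), and amend 10.9, Table 7 and section 11 to match.

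In either case, replace the one-or-more phrase in section 7 with the chosen rule, and limit claims of a confirmed mechanism to hypotheses that pass it. Align the time points in S1 with those at which the battery is collected.

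The cost is protocol wording and an adjustment step in the analysis, with no new data and no change in recruitment. The downside is that a single unadjusted hit on a non-primary measure could no longer be presented as a confirmed mechanism. Option B also makes the Stroop comparison itself stricter.

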7.1 Mechanisms pathway

The study aims to test two domains of mechanistic pathways for the FIRST protocol: a) cognition and b) quality of memories.

People experiencing PTSD, and CPTSD, report maladaptive appraisals towards themselves (negative self-concept) which increases the number, and severity, of PTSD symptoms, and particularly those related to shame, guilt, dissociation [60] and dysfunctional cognitions about oneself in relation to the traumatic event [61, 62]. Current literature on mechanisms of well-established trauma related interventions identifies that changing maladaptive appraisals is an important constituent of a positive treatment outcome [63]. We hypothesise that changes in maladaptive appraisals towards oneself (negative self-concept) is also a key cognitive mechanistic pathway for the FIRST protocol. In addition, veterans with PTSD/CPTSD exhibit more temporal fluctuations in self-esteem, negative affect, and gratitude, with a smaller effect for positive affect compared to veterans without PTSD; this diminishes their well-being [64]. Our study's qualitative data demonstrated that self-esteem could be a potential non-trauma related outcome after treatment [25]. Therefore, we first hypothesise that cognitive mechanisms pathway for the FIRST protocol involves changes in maladaptive appraisals towards oneself resulting in reduced PTSD symptomatology (guilt/shame/dissociation/dysfunctional cognitions).

Veterans with PTSD present higher rates of impulsive and emotionally charged, uncontrolled, aggression and hostility compared to veterans without PTSD. A diminished capacity for emotion regulation is also evident in PTSD samples [65, 66]. In a veteran sample, emotion dysregulation fully mediated the relationship between PTSD severity and impulsive aggression [67]. The FIRST Protocol involving techniques to work on regulating emotions related to aggression, and irritability; both in PTSD/CPTSD symptoms [62]. Emotional regulation is hypothesised to be a cognitive mechanism for the FIRST protocol since it provides veterans with the required skills and cognitions for regulating their emotions, and particularly symptoms of hypervigilance, aggression, irritability, reactivity and dissociation. We therefore hypothesise that improved emotional regulation is a

cognitive mechanism pathway for the FIRST protocol.

Impairments in memory and executive control functions are among the most consistent cognitive deficits in PTSD [68]. A meta-analysis of 60 studies demonstrated that verbal learning and memory, speed of processing, and attention/working memory showed the largest effect sizes [69]. Deficits in declarative memory are most often observed. PTSD literature demonstrated: a) verbal memory impairments (VM), b) disassociation between verbal and visual memory (impaired verbal, intact visual memory), and inconsistencies on either both forms of memory impaired, or both remaining intact [70]. Producing emotionally processed or integrated traumatic memories is likely to be an important mechanism of change for reducing intrusions and re-experiencing of the traumatic event, or from the dissociation that occurs in CPTSD leading to depersonalisation or derealisation, significantly affecting self-concept. Dissociation is a mental process where a person disconnects from their thoughts, feelings, memories or sense of identity. The FIRST protocol achieves that by double disassociation, which requires the client to observe a 'here and now' self (dissociation) observe a 'there and then' self (double dissociation) experiencing the trauma memory. This is then further developed by changing the visualised movie of the experience making it black and white rather than a colour movie. Each of these dissociative steps lessen the impact of the trauma memory on the client, thereby making it easier to process. According to the literature, verbal memory has a greater effect on the traumatic memory [38] [39]. This is achieved through a retelling of a revised version of the trauma memory in the final element of the FIRST protocol, the rescripting element. We therefore hypothesize that the memory mechanisms pathway involves emotionally processed or integrated traumatic memories which reduce PTSD symptoms (intrusions and re-experience of the traumatic event).

Non trauma related autobiographical memory is considered to be negatively affected in PTSD, with evidence of less specificity in autobiographical memories in those presenting with PTSD, [71] therefore we hypothesise that autobiographical memory will improve through the rescripting process in the final step of the FIRST protocol. This stage requires the client to generate a revised version of the trauma event, changing key details by removing the perpetrator or damaging object from the revised version, and, also ensuring that the revised movie has a different ending, with this ending leading to different consequences. The literature suggests that executive function, including attentional processes and processes of storing and manipulation of information of traumatic memories, present major deficits in people experiencing PTSD/CPTSD symptoms [69]. Specifically, working memory performance (WMP), which is an important cognitive function for our ability to store, retrieve and manipulate information related to trauma, plays a key role in explaining and altering symptoms of arousal in people with PTSD [72]. Interventions focusing on alterations/training of retaining and manipulating information related to traumatic memories (WMP) have shown to be effective on reducing post-traumatic stress symptoms [73]. On the other hand, attentional allocation seems to be important in the relationship between the ability to store and manipulate information and PTSD symptoms, with scholars proposing that attentional allocation may serve as the intersectional mechanism connecting working memory to trauma [74]. We therefore hypothesise that alterations in storing, retrieving and manipulations of trauma related memories reduces symptoms of hypervigilance. In addition, the ability to resist interference from trauma related stimuli is negatively impacted in people with PTSD/CPTSD. As examples, Scott et al. (2015) [69] meta-analysis examined a broad range of cognitive domains and found small to medium effect sizes (range, Cohen's d = -0.29 to -0.62) for PTSD as an independent variable, with the largest effects sizes in the domains of verbal learning (Cohen's d = -0.62), information processing speed (Cohen's d = -0.59), and attention/working memory (Cohen's d = -0.50) [75]. We therefore hypothesise that alterations on veterans' ability to resist and avoid interference from negative stimuli (attention) is an active ingredient of FIRST in improving symptoms of PTSD/CPTSD in veterans.

7.2 Research impact

This research will be the first to test therapies incorporating NLP and cognitive techniques process under robust trial conditions and increase understanding for its mechanistic pathway. It will thereby deliver evidence to the neurocognitive, psychiatric and psychology clinical communities on how these, almost always, brief interventions could be understood and targeted in clinical practice. Understanding mechanisms using well documented science is key to enabling these communities to be curious about, and develop greater trust in, therapies incorporating NLP techniques and reconsolidation process.

Table 1. Primary hypotheses. Testing these will allow us to achieve our primary objective of determining what specific psychological mechanisms explain the FIRST protocol's effectiveness.

Hypothesis [H]	Mechanism	Level and prediction (P=psychological hypothesis; S=symptom hypothesis)	Executive function	Psychological Assessment Task	PTSD Symptoms
H1: FIRST improves ability to remember and reproduce emotionally free neutral memories	Emotionally processed or integrated traumatic memories reduce dissociation and PTSD symptoms	At psychological level (P1): The treatment group compared to controls will experience improved trauma memories	Memory	The Trauma Memory Quality Questionnaire (TMQQ)	Dissociation, intrusions and re-experience PCL-5 Dissociative Experiences Scale- II (DES- II)
H2: FIRST improves ability to resist interference from negative stimuli resulting to improved attentional focus and inhibitory control	Alterations in ability to resist interference from distracting stimuli, and therefore effectively move attention away from trauma.	At psychological level (P2): The treatment group compared to controls will experience improved attention focus and inhibitory control	Selective Attention: Attentional facilitation, interference and avoidance Inhibitory control	Emotional Stroop task	Hypervigilance- and arousal PCL-5 (DES-II)
H3: FIRST improves regulation of emotions in relation to the traumatic event	Improves ability for regulating emotions and PTSD	At psychological level (P3): The treatment group compared to the controls will show improved self-regulation	Emotional regulation	Cognitive Emotion Regulation Questionnaire– Short (CERQ- Short form)	Aggression, irritability and reactivity PCL-5 DES-II

H4: FIRST improves self-appraisal and reduces negative appraisals in relation to self and increases access to specific autobiographical memories	Facilitates improvement in autobiographical memory and alterations on overall value that one places on oneself as a person, the tendency to have a negativistic cognitive/explanatory style and to focus on negative aspects of the self and beliefs about the causes of events in one's life	At psychological level (P4): The treatment group, compared to the control will show improved self-appraisal and autobiographical memory which will result in improvements in trauma related appraisals (shame, fear, anger) and non-trauma related outcomes (self-esteem)	Negative cognitions to self	Post-traumatic Cognitions Inventory Scale Autobiographical Memory Task (AMT) The Self-esteem scale	Guilt, shame, dysfunctional conditions PCL-5 DES-II
H5: FIRST improves executive functioning by improving WM (Working Memory) processes which reduce PTSD symptoms	Alterations in storing, focusing attention on, and manipulating information of traumatic memory.	At Psychological level (P5): The treatment group compared to control will show improved storing, encoding and retrieval of traumatic memories	Working Memory	Digit forward & backward task	Arousal Intrusions PCL-5 DES-II
The above reductions will correlate with the level of symptom improvement that patients experience following FIRST.	E/A*	At symptom level (S1): Changes (between time 1 and time 2) in the measures of intrusive memories, avoidance, self-regulation, negative appraisals, and hypervigilance will predict reductions in PTSD and dissociation symptoms.	Group Covariates of task summaries	PCL-5 DES-II	N/A*

*E/A: explained above

8 Trial design

A single centre, individually randomised clinical trial to determine the efficacy of FIRST compared to waiting-list control on PTSD symptom severity at 20 weeks. The trial is preceded by a FIRST proof of concept trial and incorporates a mechanistic evaluation.

